19.1 Laboratory trials sample size

For laboratory trials, estimations of the sample size required are dependent on the variability of PE between individuals. As such, a range of sample sizes were calculated that took both this, and variability in the confidence intervals around the estimate, into consideration (Table 3). A conservative estimate of the PE standard deviation of 30 % was chosen, which when allowing for a confidence interval of ± 15 % around the estimate, gives a sample of 16 people. When allowing for 5 % loss-to-follow-up, the total sample size will be 17 people. Equal numbers of male and female participants are preferred.

Table 3. Estimation of sample size for determining the Protective Efficacy of repellent products in laboratory trials.

		Standard deviation of Protective Efficacy					
		10 %	15 %	20 %	25 %	30 %	35 %
Margin of error (CI)	5 %	16	35	62	97	139	189
	10 %	4	9	16	25	35	48

	15 %	2	4	7	11	16	21
	20 %	1	3	4	7	9	12

For stage two laboratory trials (repellent product persistence), multiple follow-ups on the same individuals will generate more repeat data points. As such, the sample size requirement for PE will be sufficient. If we observe in stage one that variability between individuals was much greater than expected then we will consider increasing the sample size for stage two.

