19.2 Field trials sample size

This trial will be powered to detect a protective effect in the intervention (treatment) groups relative to the control groups. To test for 30 % protection (PE) in the intervention arm versus the control arm, assuming a standard deviation of 30% and using 90 % power, 23 children are required in each study group. When allowing for 25 % loss-to-follow-up, the total sample size in each study arm will be 29 people. Equal numbers of male and female participants are preferred.

Not all approximately participants in the wearable repellent device arms of the field trial will be interviewed for intervention acceptability. Based on previous experience, we anticipate that a sample of 15 to 20 child-caregiver pairs, purposively sampled to represent the range of child ages will be sufficient, and further data collection unlikely to yield additional information. However, we will review our data regularly during the data collection process and will adjust the sample accordingly.

20 Enrolment, randomisation and allocation

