21.1.3 Topical repellents

21.1.3.1 Protective Efficacy

Consenting participants will be asked to avoid the use of fragranced cosmetic or washing products for 12 hours prior to each laboratory trial. Immediately before testing, the participant's arm will be washed with unscented soap, rinsed with water, rinsed with 70 % ethanol in water, and towel dried. An analytical standard of the repellent will be tested at five incrementally increasing doses up to a maximum of 20 %, each diluted in ethanol.

For the first test, the diluent alone (1.4 ml) will be tested as a control. This will be applied to the participant's arm and allowed to dry for one minute. The participant will then insert his/her arm into a purpose-designed insect cage, with a hole in the top allowing a camera lens to film the upper surface of the hand and arm. The cage will contain 100 test insects, and insect behaviour on the arm will then be filmed for ten minutes. This video footage will retrospectively be analysed for the number of fly contact, and the total duration of fly contact. The participant will be instructed to refrain from moving his/her arm, which will disturb landing flies.

For the test to proceed, there must be five or more fly contacts, with the diluent (control,) in the ten-minute observation period. After this, the participant will remove their arm from the cage, carefully brushing off any flies as they leave. The lowest dose of repellent in ethanol (1.4 ml) will then be applied to the arm and allowed to dry for one minute. The participant will then re-insert his/her arm into the cage with the test insects, and insect behaviour on the arm will again be filmed for ten minutes.

This procedure will be repeated for each incremental dose of the repellent, up to a maximum of 20 % active ingredient. Each dose will be tested serially and without delay. To determine the repellent dose, the doses applied to reach that which was effectively repellent will be summed. If at any point the fly-arm contact rate drops below five in 10 minutes, the test will be stopped. After all repellent doses have been tested, 1.4 ml of the diluent control will be applied to the participant's other arm, and tested again as per the first ten-minute test, in order to verify continued fly contact/landings. If at this point there are less than five fly contacts, the results of the experiment will be discarded.

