21.2 Field trials

21.2.1 Test insects and testing site

Participants will be exposed to fly-face (including eye, nose and mouth) contacts outside their house. Previous studies indicate that the majority of such contacts will be *Musca sorbens*, although *Musca domestica* may be present (46); data thus far from our field site corroborates this prediction. Ambient temperature and humidity will be recorded at every fly-face observation period. Testing will be started between 09:00 and 10:00, as preliminary data from the same locality indicate that *M. sorbens* are less active earlier in the day, allowing for the six-hour testing duration. Should the fly density at the time of year of testing be very high, the test durations may be shortened (e.g. to five minutes), as a robust measure of protection will be obtained in a shorter interval.

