26.3 Data analysis

26.3.1 Protective Efficacy, p

The protection (protective efficacy, p) afforded by a repellent product will be presented as a percentage. p will be estimated by comparing fly-arm contact duration and fly-eye contact frequency, in laboratory and field trials respectively, after application (or wearing) of the repellent product to that during the control period.

Equation 1. Protective Efficacy, p

$$p = 100 \times ((C - T)/C)$$

Where (laboratory trials):

- C is the total duration of fly-arm contact before application of repellent ('control' measure), and
- T is the total duration of fly-arm contact after application of repellent ('treatment' measure)

Where (field trials):

- C is the frequency of fly-eye contacts before application of repellent ('control' measure), and

- T is the frequency of fly-eye contacts after application of repellent ('treatment' measure)

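### Field protective efficacy is a per-child ratio on one control count, with no minimum and no zero rule; at modest contact counts it understates absolute efficacy, and the 30% SD behind the power is unsupported

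*Combined protocol and SAP*

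**What the plan says.** Section 26.3.1 (Equation 1) sets p = 100 x (C - T)/C. In the field, "C is the frequency of fly-eye contacts before application of repellent", and T is the same measure after application. In the laboratory both terms are total contact duration.

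Equation 1 does not say whether p is calculated for each child and averaged, or once from totals. The sample-size sections point to the first. Section 19.1 says that "estimations of the sample size required are dependent on the variability of PE between individuals". Section 19.2 sizes the comparison of each product group with the no-product group for a 30-point effect: "assuming a standard deviation of 30% and using 90 % power, 23 children are required in each study group". An SD of PE needs one value of p per child.

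For a laboratory test to go ahead, "there must be five or more fly contacts, with the diluent (control,) in the ten-minute observation period" (section 21.1.3.1). No matching field rule is given. Field windows are ten minutes by default, but at very high fly density "the test durations may be shortened (e.g. to five minutes" (section 21.2.1). Section 16.2.2 says that field PE, not laboratory PE, will inform which repellents enter the Phase 3 trial.

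**The concern.** A single ten-minute count is a noisy denominator. When C is low by chance, (C - T)/C becomes strongly negative; when C is high by chance, it cannot exceed 100%. The average over children is therefore pulled below the true reduction and its SD is inflated. A child with C = 0 has no value at all, and the plan does not say what happens to that child.

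Two things are at stake. The absolute field PE informs selection for Phase 3, so understating it could count against a useful product. The power of the between-arm comparison depends on an SD of 30%, and the ratio may not have that SD.

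**Working it through.** **The plan's own figure.** Inputs from section 19.2: difference 30 points, SD 30%, power 90%. Alpha is not stated; two-sided 0.05 is assumed. The normal formula gives n = 2 x (1.960 + 1.282)^2 x (30/30)^2 = 21.0, so 22 per group. The two-sample t solution is 22.02, so 23, with power 91.2% at 23. The stated 23 is reproduced, and 23 x 1.25 = 28.75 gives the 29.

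**Bias of the averaged ratio.** Assume independent Poisson counts with mean m in the control window and (1 - PE) x m in the test window, and leave out children with C = 0. Then

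mean of p = 1 - (1 - PE) x k, with k = m x E[1/C given C > 0].

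The values of k are 1.289, 1.130, 1.056 and 1.026 at m = 5, 10, 20 and 40. At m = 5, for example, 1 - 0.7 x 1.289 = 0.098. Power is for a t-test on per-child p with 23 per arm, by simulation.

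| Mean control contacts | True PE 30% reads as | True PE 0% reads as | Arm difference (30 x k) | SD, no effect | Power |
|---|---|---|---|---|---|
| 5 | 10% | -29% | 39 points | 112% | 28% |
| 10 | 21% | -13% | 34 points | 64% | 58 to 59% |
| 20 | 26% | -6% | 32 points | 36% | 91 to 92% |
| 40 | 28% | -3% | 31 points | 24% | over 99% |

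At these counts k exceeds 1, so the arm difference is slightly inflated rather than attenuated. The power is lost through the SD.

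**Zero counts.** The chance of C = 0 is exp(-m): 13.5% per child at m = 2, 0.7% at 5, and under 0.01% at 10. Below a mean of about 1.5, leaving out the zeros reverses the bias: at m = 1, k = 0.767 and a true 30% reads as 46%.

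**Variation beyond Poisson.** The documents give no figure for this, so these are illustrations. Power with 23 per arm:

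- True ratio varying between children (SD 0.2): 79% at 20 contacts, 89% at 30, 95% at 50.
- Fly density varying between children (gamma, shape 2): 65% at 20, 80% at 30, 93% at 50.
- Overdispersion between a child's own windows (negative binomial, k = 10): 43% at 20, and only 63% at 100. Here a true 30% still reads as about 21% at 100 contacts.

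**Alternative estimator.** Under Poisson counts, 1 - sum(T)/sum(C) averages 29.4%, 29.7% and 29.8% at 5, 10 and 20 contacts for a true 30%. It gives 29.7% in the overdispersed case at 100. A per-child log ratio with 0.5 added has power of 38%, 69% and 94% at 5, 10 and 20. The bias goes; low power at low counts does not.

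**The case against.** The strongest reply is that nothing in the protocol says the counts are small. The site is to be chosen for abundant flies (sections 13.2 and 14.3), and a ten-household pilot checks whether density is suitable (section 21.2.2). With 40 or more contacts and near-Poisson variation, the problem almost disappears. This stands, and it makes the point conditional. It does not remove the point: no expected count is given, the pilot check has no threshold, and high counts do not help if windows are overdispersed.

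Second, Equation 1 does not state its unit, and section 26.3.3 speaks of total frequency. Applied to summed counts, Equation 1 is one of the remedies below. If that is meant, the plan should say so and explain how the SD of PE in section 19.2 relates to it.

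Three stronger readings are tempting, and the documents do not support them:

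- **That the 90% power is wrong.** The 23 per group follows from its inputs. Only the SD lacks support.
- **That good products would fail the 30% carry-forward rule by the amounts tabulated.** That rule is a laboratory one, based on contact duration with a five-contact minimum. The count calculations do not model it.
- **That an inert product would read as 50% effective.** That needs a ten-minute C set against a five-minute T in raw counts. Section 21.2.1 does not exclude this, but it does not plan it either. Shortening both windows equally, or reading frequency as a rate, removes the distortion.

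**Conclusion.** The concern holds in a conditional form. If field PE is averaged over per-child ratios, as the sample sizes imply, it understates a true 30% by about 20, 9, 4 and 2 points at means of 5, 10, 20 and 40 contacts per window. It is undefined for a child with no control contacts. With Poisson noise alone, the ratio needs roughly 20 or more contacts per window to come near the planned SD of 30%, and about 30 to 50 with moderate extra variation between children. The test against the no-product arm is not biased towards no effect at these counts; it loses power.

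This rests on per-child calculation, on Poisson or gamma-Poisson counts, on two-sided alpha of 0.05, and on a range of counts that the documents neither give nor exclude. The absence of a field minimum and of a rule for C = 0 does not depend on any of these assumptions.

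**What to change.** In section 26.3.1, define field PE as 100 x (1 - rate ratio) from a log-link count model (negative binomial or quasi-Poisson) with a participant effect, a period-by-arm term and log(minutes observed) as offset. A simpler alternative is 100 x (1 - sum(T)/sum(C)) with a participant-level bootstrap interval, each sum being divided by minutes observed if windows differ. Either keeps children with C = 0 without an ad hoc exclusion.

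In section 21.2.1, state that control and test windows for a given child have the same length.

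In section 19.2, give the basis for the 30% SD, and check it with the pilot, which observes ten children before and after diluent alone. Ten children give only a rough SD: assuming normality, the 95% limits are the estimate times sqrt(9/19.02) = 0.69 and sqrt(9/2.70) = 1.83, so an observed 30% fits roughly 21% to 55%. The mean count and the spread between paired windows should therefore be reported as well. If the SD does not hold, restate the power.

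The cost is analysis wording. No added data collection is needed, though the stated power may have to come down, because the better estimator does not restore 90% at low counts.

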26.3.2 Median Complete Protection Time (mCPT)

Median CPT will be estimated in stage two ('persistence') laboratory trials only, for those repellents that demonstrated more than 30 % PE. The complete protection time for a specific dose will be estimated as the time elapsed until the first fly landing on the arm in each replicate, and based on repeat estimates of CPT, the mCPT will be estimated using a Kaplan-Meier function.

26.3.3 Median Effective Dose (ED₅₀) and Median Effective Time (ET₅₀)

ED₅₀ and ET₅₀ will be calculated in stage two ('persistence') laboratory trials, however, as only one dosage level will be used in the field only ET₅₀ will be estimated there.

The relationship between Protective Efficacy and repellent dose and time since treatment can be estimated using a probit-plane regression model (Equation 2). The coefficient b_1 provides an estimate of the effect of repellent dose on p , and b_2 provides the effect of the time since treatment on p .

Once these coefficients have been estimated, then we can estimate the ED₅₀, concentration (dose) of repellent product that affords 50 % protection from fly contacts at time zero (the time of application). This is done by setting $p=0.5$ and $t_1=0$ and then solving equation 2. We can also estimate ET₅₀, estimating the persistence of the protective effect of a repellent product for a given dosage, using the same method.

Equation 2. Probit-plane regression model for ED₅₀ and ET₅₀

$$\ln [p / (1 - p)] = a + b_1(D_0) + b_2 t_1$$

Where:

- p is as above, estimated from
 - Total duration of fly-arm contact (laboratory trials)
 - Total frequency of fly-eye contacts (field trials)
- D_0 is the dose calculated as the natural logarithm of the dose applied ($\ln[\text{dose}]$)
- t is the time post-treatment in hours
- a , b_1 and b_2 are coefficients estimated using the probit-plane regression model

In the laboratory trials, p will be estimated by the total duration of fly-arm contact, while in the field trials p will be estimated using the total frequency of fly-eye contacts, as defined in section 26.3.1.

27 Monitoring

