Study type: This is a within-subject, non-masked, trial of the use of commercially available insect repellents against *Musca sorbens*, with two consecutive participant groups in the laboratory and in the field, and a primary endpoint of measuring the protective efficacy of each repellent product.

Study design:

1. Laboratory trials
 - a. Target sample size: 17 participants (all participants test all product iterations)
 - b. Stage 1. Protective Efficacy. Determining the protection of repellent products. Only those products/concentrations that protecting against at least 30 % of fly contact will be carried on to stage 2.
 - c. Stage 2. Persistence. The persistence of effect will be measured over a six-hour period. For slow-release wearable repellent technologies, this period will be extended for follow-up at 1, 2, 3 and 4 weeks. Estimations of persistence will allow final selection of repellent products/concentrations to be tested in the field trials
2. Field trials
 - a. Target sample size: 29 participants per study arm (each participant tests only one product iteration), 10 participants in the Pilot Phase
 - b. Up to four groups (study arms) will test the effectiveness of only one topical repellent or slow-release wearable repellent device, at one concentration, against a control group who will receive no intervention.

Intervention: Repellent products will be chosen from: DEET (N,N-diethyl-3-methylbenzamide), IR3535 (3-[N-butyl-N-acetyl]-aminopropionic acid ethyl ester), Picaridin (2-(2-hydroxyethyl)-1-piperidinecarboxylic acid 1-methylpropyl ester); PMD (para-Mentane-3,8-diol) or permethrin (m-Phenoxybenzyl)-cis,trans-3-(2,2-dichlorovinyl)-2,2-dimethylcyclopropanecarboxylate). Products tested will be either (1) topical repellents, or (2) in long-lasting, plastic formulations of repellents that can be worn on the body (wearable repellent technologies). The insect repellent synergist Vanillin (4-Hydroxy-3-methoxybenzaldehyde) may be added to the long-lasting plastic formulations, to improve the duration of protection.

Main study outcomes/endpoints: Protective Efficacy, Complete Protection Time, Median Effective Time and Median Effective Dose

Key inclusion criteria (Laboratory trials, LSHTM):

Ages eligible for study: 18 years and \leq 65 years

Sexes eligible for study: both

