21.1.3.2 Persistence

Having established which repellent products are effective at which doses, the persistence of all repellent products at doses achieving at least 30 % protection (at time zero) will be determined. Persistence will be determined using an extended version of the protocol described in 21.1.3.1. Preparation, and control testing, will be conducted in the same manner, then the repellent products at the appropriate dose will be applied and tested for ten minutes as previously, and the observation will be repeated every hour for six hours (Figure 5). After testing, the participant will be given access to washing facilities to wash off the topical repellent. This data will allow calculation of the Median Protection Time/Effective Dose (ET_{50} and ED_{50}). To determine the Median Complete Protection time (mCPT), the same protocol will be used however the first test sampling period will be extended until the first fly-arm contact.

[figure not shown]

Figure 5. Timescale for repellency complete protection time (CPT), and median protection time, testing in the laboratory.

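### ED50 is to be estimated from stage 2, which keeps only doses with at least 30% PE, so a product that keeps one dose has no estimable ED50 although stage 1 has measured several doses at time zero

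*Combined protocol and SAP*

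**What the plan says.** - **Where ED50 is estimated.** Section 26.3.3 says that ED50 and ET50 "will be calculated in stage two ('persistence') laboratory trials". Section 21.1.3.2 says of the persistence readings: "This data will allow calculation of the Median Protection Time/Effective Dose". Section 13.1 also lists ED50 among the stage 2 results.
- **What ED50 is.** It is the dose that solves Equation 2 with p = 0.5 and time zero (26.3.3). It is a named secondary outcome for the laboratory trials (17.2) and serves the secondary objective of comparing products (12.2).
- **What enters stage 2.** The Summary states: "Only those products/concentrations that protecting against at least 30 % of fly contact will be carried on to stage 2". Section 21.1.3.2 states that "the persistence of all repellent products at doses achieving at least 30 % protection (at time zero) will be determined". The filter therefore acts on each dose as well as on each product.
- **What stage 1 holds.** Section 21.1.3.1 states: "An analytical standard of the repellent will be tested at five incrementally increasing doses up to a maximum of 20" per cent. The other four levels are not given. Doses go on serially, the run ends early if contacts fall below five in ten minutes, and the applied doses are added up. Section 13.1 gives stage 1 only a selection role.
- **What is absent.** Nothing puts stage 1 readings into Equation 2, sets a minimum number of retained doses, or says what is reported if one dose passes.

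**The concern.** ED50 needs a dose slope, and a slope needs at least two doses. The plan takes the slope from the stage in which low doses have been removed, and leaves out the stage that observes the time-zero dose-response directly. A product passing at one dose would have an ET50 at that dose but no ED50.

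Such failures would not be random. They would fall mostly on weaker products, so the comparison of products by ED50 would lose its weaker members selectively. Section 21.1.3.1 sets the threshold at 30% rather than 50% on the ground that smaller reductions may still matter. The plan therefore expects to carry forward products whose ED50 may lie near or above the 20% maximum.

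**Working it through.** **1. The plan's own figure.** Section 19.1 uses an SD of PE of 30% and a margin of ±15%. With z = 1.96 (level inferred), n = (1.96 × 30 / 15)² = 15.4, rounded up to 16, and 17 after 5% loss. This reproduces the plan. The size is set for the precision of PE, and no figure is given for ED50.

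**2. Estimability.** Equation 2 is ln[p/(1−p)] = a + b1·ln(dose) + b2·t, so ln ED50 = −a/b1. With one dose d, a + b1·ln(d) is a single constant. The hourly readings estimate that constant and b2, but cannot split a from b1. Adding participants or hours does not help.

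**3. How often fewer than two doses pass.** Assumptions not in the documents: the dose grid, b1 from 0.7 to 1.5, the true ED50, and a filter applied to the observed mean PE of 16 people. The SE of that mean is 0.30/√16 = 0.075.

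- True PE at dose d: p = 1/[1 + (ED50/d)^b1].
- Chance that d passes: q = Φ((p − 0.30)/0.075).

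Example: doubling grid 1.25, 2.5, 5, 10, 20%; b1 = 1; ED50 = 20%.

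- p = 0.06, 0.11, 0.20, 0.33, 0.50
- q = 0.001, 0.006, 0.09, 0.67, 0.996
- P(none pass) = 0.001. P(exactly one passes) = 0.30, nearly all of it the 20% dose alone.

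| Assumed grid | ED50 7% | ED50 14% | ED50 20% | ED50 30% |
|---|---|---|---|---|
| Doubling, 1.25–20% | about 0 | 0.01–0.15 | 0.08–0.69 | 0.36–0.97 |
| Equal steps, 4–20% | about 0 | about 0 | at most 0.02 | 0.02–0.64 |
| Tenfold, 0.002–20% | 0.53–0.99 | 0.90–1.00 | 0.96–1.00 | 0.99–1.00 |

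Ranges run over b1 = 0.7 to 1.5, and steeper slopes give the higher values.

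**4. Precision when ED50 can be estimated.** Delta method on the doubling grid: each mean logit has weight 16·[p(1−p)/0.30]², errors are independent, and b2 = −0.4 per hour. Entries are the SE of ln ED50. Stage 1 means five doses at time zero. Stage 2 means the doses with true PE of at least 30%, at seven time points each.

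| b1, ED50 | Doses kept | Stage 1 | Stage 2 | Pooled |
|---|---|---|---|---|
| 1, 14% | 2 | 0.21 | 0.17 | 0.13 |
| 1, 20% | 2 | 0.26 | 0.21 | 0.16 |
| 1.5, 20% | 1 | 0.19 | none | 0.12 |
| 1, 30% | 1 | 0.39 | none | 0.27 |

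An SE of 0.39 means 95% limits within a factor of exp(1.96 × 0.39) = 2.1. For true ED50 up to 20% with two or more doses kept, the SE is 0.09–0.33 from stage 2 (b2 from −0.3 to −0.6) against 0.13–0.36 from stage 1. Where ED50 lies above the tested range and stage 2 still keeps two or more doses, it is 0.48–0.64 against 0.37–0.48. The pooled figures assume complete stage 1 runs on the same dose scale as stage 2, with no stage or session terms. Those terms would widen them.

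**5. Simulation check.** 17 participants, doubling grid, b1 = 1, ED50 20%, participant and residual SD 1 on the logit scale. The entries are 95% ranges of estimated/true ED50.

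- Five stage 1 doses at time zero: about 0.58 to 2.0.
- Doses 10% and 20%, seven readings each, independent errors: 0.59 to 1.89.
- The same with an added session SD of 0.7: about 0.50 to 3.7. With 1.0: about 0.33 to 7.2. The upper tail is poorly determined, and repeat runs gave higher upper limits.

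**The case against.** **With two or more doses, stage 2 does the job.** This stands if errors are independent. A reader might infer that cutting low doses makes ED50 unstable in general. Fitting only the time-zero readings at 10% and 20% does give 0.41 to 10.9 times the truth at ED50 20%. But section 21.1.3.2 repeats the reading hourly for six hours and Equation 2 uses all of them, which brings the range to about 0.6 to 1.9. That stronger reading is not supported. The reservation is that each stage 2 dose needs its own six-hour session, so between-session variation enters the dose contrast. Stage 1 doses are compared within one run.

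**Stage 1 is not a clean five-dose set.** This also stands. Doses are applied serially to one arm, and "the doses applied to reach that which was effectively repellent will be summed". On the doubling grid the total by the last step would be 1.25 + 2.5 + 5 + 10 + 20 = 38.75, not 20. Dose is tied to order, and "If at any point the fly-arm contact rate drops below five in 10 minutes, the test will be stopped", so upper doses can be missing because the repellent worked. These features call for stated rules, but do not justify leaving the data out. The stop acts mainly on strong products or runs with few control contacts, whereas stage 2 fails on weak products, whose stage 1 runs are more likely to be complete.

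**The one-dose case may be rare, and ED50 is one secondary measure among several.** On an equal-step grid it is rare up to ED50 20%. The grid is not stated, so it cannot be excluded. ET50 and mCPT also compare products, and section 16.2.2 has the field results inform the later trial, which limits the consequence.

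**Conclusion.** The point holds in a limited form. Under the stated analysis, a product that keeps one dose has no ED50; this is algebra and rests on no assumption. How often it happens depends on the unstated grid, the slope and the potency. It is negligible for potent products on doubling or equal-step grids. It is appreciable on a doubling grid when ED50 is near or above 20%, and likely on a tenfold grid from ED50 7% upwards.

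With two or more doses kept, precision is similar to that of five stage 1 doses if errors are independent, and worse if readings within a session are correlated. When ED50 exceeds 20%, five doses also extrapolate; they still give an estimate, but it should be labelled as outside the tested range. The correction is worth making because the data are already planned and the failures would fall selectively on weaker products.

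**What to change.** In section 26.3.3, state that:

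- ED50 and b1 are estimated from the stage 1 time-zero readings pooled with the stage 2 readings, while b2 and ET50 rest mainly on stage 2;
- D0 is the logarithm of the cumulative amount applied at each reading;
- the model has participant and session effects, and a stage term to absorb serial-order differences, and the text says to which stage's level the reported ED50 refers;
- runs stopped below five contacts stay in with the readings obtained, including the one that triggered the stop;
- an ED50 beyond the highest tested dose is reported as above the tested range.

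Add a sensitivity analysis from stage 2 alone wherever two or more doses remain. List the five dose levels once they are fixed, so that the risk can be judged before stage 1.

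The cost is analysis wording and a slightly more complex model, with no extra participants or visits. The downside is reliance on summed serial doses being comparable with a single application. The sensitivity analysis checks this only for products that keep at least two doses. For a one-dose product the result rests on the stage 1 slope and should be reported as such.

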13.2 Field trial

In the field clinical trial, eligible participants will be randomised between groups (study arms), each of which will test only one topical repellent or slow-release wearable repellent device, at one concentration. A maximum of four groups will be tested in addition to a control group, and each group will contain 29 children between the ages of three and 12 years. The additional control group, receiving no product, will allow for temporal comparison of fly contact across a day of testing.

The combination of product and product format to be tested will be determined before the study commences. The PE will be determined by measuring the frequency of fly-eye, fly-nose, fly-mouth and fly-face contacts by *Musca sorbens* after application of the product, in a 'field' environment where these flies are naturally present at high density. Control measurements will be taken of fly contact on each participant prior to this. Test measures will be repeated over a period of six hours to determine the ET_{50} , and for wearable repellent devices, participants will continue to wear the

product and tests will be repeated at one, two, three and four weeks later. Topical repellents will be applied by the Stronger-SAFE field team nurses, who will also demonstrate how to wear the repellent devices. A qualitative assessment of acceptability and barriers to use will be carried out at the end of the trial.

14 Study setting and populations

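### Day-one field ET50 compares each hourly reading with one pre-application reading and leaves out the no-product arm; Equation 2 also lacks a fitting level and a rule for p below zero

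*Combined protocol and SAP*

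**What the plan says.** Section 26.3.1 defines p = 100 × (C − T)/C. In the field, C is the frequency of fly-eye contacts before application and T the frequency after it. Protection "afforded by a repellent product will be presented as a percentage".

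Section 26.3.3 then says: "The relationship between Protective Efficacy and repellent dose and time since treatment can be estimated using a probit-plane regression model (Equation 2"). The printed form is ln[p/(1 − p)] = a + b₁·ln(dose) + b₂·t, solved at p = 0.5. In the field "p will be estimated using the total frequency of fly-eye contacts", and "as only one dosage level will be used in the field" only ET50 is estimated there.

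On day one, sections 21.2.3 and 21.2.4 take one control reading, then a test reading straight after application, then five hourly readings. At the weekly device visit the device is removed and a fresh control reading is taken.

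On the no-product arm, section 13.2 says it "will allow for temporal comparison of fly contact across a day of testing". Section 19.2 adds: "This trial will be powered to detect a protective effect in the intervention (treatment) groups relative to the control groups".

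**The concern.** On day one, hours since application and time of day advance together. With a single early control reading, the time slope in Equation 2 contains both the loss of repellency and any change in fly activity. The arm that could separate them exists, but no formula uses it. ET50 is a secondary outcome (section 17.2), and section 16.2.2 says field outcome measures will inform inclusion in the Phase 3 trial, so its absolute value matters.

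The smaller concern is Equation 2 itself. Equation 1 gives a negative p when T > C, and no p when C = 0. Section 26.3.3 does not say whether p is taken per participant or pooled, whether the logit transforms observed p or links to expected p, or what happens to such readings. Two analysts could report different ET50s from the same videos.

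**Working it through.** **1. The plan's own figure.** Section 19.2 gives 23 per arm for a 30-point difference, SD 30, 90% power. Assuming two-sided 5% (not stated), the normal formula gives 2 × (1.96 + 1.28)² × (30/30)² ≈ 21.0, rounded up to 22. The t-test version gives 22.02, rounded up to 23. Then 23 × 1.25 = 28.75, so 29. The stated figure reproduces as a comparison between a product arm and the control arm. That comparison does not appear in section 26.3.

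**2. Drift, by algebra.** Let true protection follow logit PE(t) = s(2 − t), so true ET50 is 2.0 h. Let fly activity change as exp(d·t) after the control reading. Equation 1 then crosses 50% at the first t where

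[1 − PE(t)] × exp(d·t) = 0.5, with 1 − PE(t) = 1/(1 + exp(s(2 − t))).

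Check at s = 1, d = +0.10, t = 1.69: 0.423 × 1.184 = 0.50. Check at d = −0.10, t = 2.62: 0.650 × 0.770 = 0.50.

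| Assumed change per hour | Crossing, s = 1 | Range, s = 0.5 to 1.5 |
|---|---|---|
| +10% | 1.69 h | 1.46–1.78 h |
| +5% | 1.83 h | 1.68–1.88 h |
| none | 2.00 h | 2.00 h |
| −5% | 2.24 h | 2.15–2.55 h |
| −10% | 2.62 h | 2.36 h or later (s = 0.5: not crossed by 12 h) |

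These need no assumption about counts.

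**3. With the no-product arm.** The factor exp(d·t) multiplies T/C in both arms, so it cancels in 1 − (T/C product)/(T/C no product) at the same hour. Simulations used 23 children per arm, mean 10–50 contacts, dispersion 0–0.25 and readings at 0–5 h. Median ET50 was 1.94–2.06 h at +10% and 1.98–2.11 h at −10% (s = 1), 1.75–2.11 h at ±10% over all slopes, and 1.83–2.05 h without drift.

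**4. Out-of-range p.** With the plan's SD of 30 points and a normal approximation, P(p ≤ 0) = Φ(−30/30) = 15.9% at mean PE 30%, and Φ(−20/30) = 25.2% at mean PE 20%. In the field simulations without drift, T > C occurred in 4–26% of readings, and still 4–26% at mean 50 contacts. C = 0 occurred in 0–2%.

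Median ET50 (true 2.0 h, no drift) by handling:

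| Handling | Field, 23 children | Laboratory, 16 people, mean 20–50 contacts |
|---|---|---|
| Delete out-of-range readings | 1.96–4.79 h | 2.04–4.43 h |
| Clip each p to 0.01–0.99 | 0.92–2.23 h | 0.97–2.35 h |
| Per-participant logit link, T > C set to 0 | 1.57–2.40 h | 1.65–2.58 h |
| Pooled by time point, logit link | 1.89–2.10 h | 1.97–2.20 h |

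The laboratory requirement, "For the test to proceed, there must be five or more fly contacts", rules out C = 0 there. No such floor is stated for the field.

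**The case against.** **Drift is not shown.** Section 21.2.1 says flies are less active earlier in the day and uses this to set the 09:00–10:00 start. A reader might infer that activity keeps rising through the test and that field ET50 is therefore too short. The documents do not support that: they give no trend inside the test window, so size and direction are unknown. A rise of 10% per hour would mean about 65% more flies by hour five (exp(0.5) = 1.65), and at 5% the shift is modest. This objection stands against any stated bias, but not against using an arm recruited to detect one.

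**The arm is not ignored by the plan.** True. Sections 13.2 and 19.2 give it a purpose and a sample size. It is missing only from the formulas.

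**Equation 2 is usable.** A reader might infer that it cannot be fitted because p may be zero, negative or 100%. That goes too far. As a link on expected p, T = 0 and T = C cause no difficulty, and pooling by time point recovers the true value closely. The largest errors come from deletion or clipping, which the plan does not prescribe. Setting p = 0.5 also settles the scale as a proportion. What stands is that no fitting level or T > C rule is given. Section 19.1 says "estimations of the sample size required are dependent on the variability of PE between individuals", which suggests p per person, and the word total in section 26.3.3 does not clearly mean a sum over participants.

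**The simulations start high.** A true ET50 of 2 h with slopes 0.5–1.5 implies time-zero PE of about 73%, 88% and 95%. Products may advance at 30% (sections 13.1 and 21.1.3.1). This stands, and the fix needs a rule for products that start below 50%.

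**Conclusion.** The main point holds for day-one field ET50 only: as written, the estimate cannot separate fading protection from time of day. Under assumed changes of 5% or 10% per hour, a true 2.0 h would read as 1.83 or 2.24 h, or as 1.69 or 2.62 h, at slope 1. These are illustrations, because the documents give no drift, counts or dispersion. Weekly device visits have their own control reading, and laboratory results are not affected by this point.

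The secondary point is smaller. The fitting level and the handling of T > C (and of C = 0 in the field) are unstated, and deleting out-of-range readings would generally push ET50 upward.

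A reader might also infer that the wrong product would be chosen. That is not supported. In simulations of 2 h against 3 h products without drift, the order was right in 95–100% of runs with clipping, a link or pooling, and in 77–100% with deletion. The primary efficacy definition is not challenged, and calling a logit a probit affects only the label.

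**What to change.** Amend section 26.3.3.

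**Field, day one.**
- At each hour, PE = 1 − (T/C in the product arm)/(T/C in the no-product arm), from a quasi-Poisson log-link model of raw fly-eye counts with a participant effect and arm-by-period terms.
- ET50 is the linearly interpolated time at which PE first falls below 50%.
- If PE is below 50% at time zero, report ET50 as not reached for that reason. Report it as beyond the last time point only if PE stays at or above 50% throughout.
- 95% CI by bootstrap over participants within arm.
- Weekly device visits keep their same-visit control.

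**Laboratory ET50 and ED50.**
- Compute p as a proportion from durations summed over participants at each dose and time point.
- Fit Equation 2 as a logit-link model for expected p, and call it a logit.
- Set any pooled p below 0 to 0, and delete no out-of-range readings.
- Bootstrap over participants for intervals.

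**Cost.** Analysis wording and a little more work, with the same children and videos. This assumes the no-product arm has the same baseline and hourly readings as the product arms. Section 13.2 implies this, but section 21.2 does not set out that arm's schedule and should. Field intervals will be wide: simulated 95% bootstrap widths were 0.5–2.1 h, with coverage 91–98%. If laboratory control counts are low (mean about 10), the pooled fit is still biased upward (2.07–2.70 h against 2.0 h), because the five-contact requirement raises C.
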